6.1.2 UTILIZATION AND ADMINISTRATION

IMPORTANT: These recommendations are designed only to serve as a general guideline. They are not intended to supersede institutional protocol or professional clinical judgement concerning patient care.

6.1.2.1 RECOMMENDED INSTRUCTIONS FOR USE OF THE PNEUMATIC SHORT LEG WALKERS (BOOT) & SUPPLIES (SOC DRESSINGS)

During the Screening Phase of the study, all subjects will have SOC products applied by the investigative site at the weekly visits. They will be then instructed on how to change their dressings on a daily basis. After randomization, only subjects who are randomized to the SOC cohort will continue daily dressing changes. Those subjects in either the AMNIOEXCEL Plus or Apligraf cohorts will only have their dressings changed weekly at follow-up visits until the investigator determines that their wound has closed. If the wound closes on or before week

12, offloading (if previously utilized for that subject) will continue without dressings during the follow-up period.

The off-loading boot/protective device and SOC dressings to be used in this study will be provided by the Sponsor through a specific distributor. The off-loading boot/protective device will only be used by subjects who require offloading throughout the Screening and Treatment (i.e., those subjects with study ulcers located on the plantar or lateral surfaces of the foot or any location experiencing weight-bearing or shear forces *as determined by the Investigator*). These subjects will wear the boot up to their exit from the study. The boot will be applied to the subject's foot on top of the dressings.

Application of the dressings & boot by the Investigator:

1. Gently remove any dressing previously applied to the wound and clean the area with a gentle cleanser.
2. If appropriate, debridement and hemostasis will be performed. (Note: in this study only sharp debridement will be used)
3. During Screening and for SOC-randomized subjects: Instruct the subject on the proper way to change dressing
 - a. Inspect the wound and perform study assessments as directed elsewhere
4. Apply normal saline gel to the thickness of a coin.
5. Cover the gel with a foam dressing.
6. Secure the foam dressing with conforming roller gauze.
7. Cover the roller gauze with Coban.
8. For subjects who have ulcers that require offloading, apply the boot.

Daily Changing of the Dressings by the Subject:

1. Remove boot, if applicable
2. Gently remove dressings
3. Clean the wound with tap water and pat the area dry
4. Inspect the wound
 - a. Subject will contact the site by phone if they believe there is anything wrong with the wound.
5. Apply normal saline gel to the thickness of a coin.
6. Cover the gel with a foam dressing.
7. Secure the dressings with conforming roller gauze.
8. Cover the roller gauze with Coban.
9. For subjects who have ulcers that require offloading, apply the boot.

Note: Subjects who use the offloading boot will be instructed that it is to be worn **at all times** except when bathing or sleeping.

6.1.2.2 RECOMMENDED INSTRUCTIONS FOR USE OF AMNIOEXCEL PLUS

Preparation Instructions (also found in the product's Instructions for Use supplied with the product):

1. Open carton or box containing AMNIOEXCEL Plus and remove the peel-pack.
2. Peel open the outer package and remove the inner foil pouch using aseptic technique.
Note: The inner foil pouch and its contents are sterile and may be placed directly into the sterile field.
3. Peel the inner pouch open and place the AMNIOEXCEL Plus into the sterile field. *Note: Application of AMNIOEXCEL Plus will be easier if the surface to be covered is relatively dry.*
4. Either side of the membrane may be applied to the wound surface.
5. It is sometimes necessary to gently "roll" the AMNIOEXCEL Plus at the edges to smooth out wrinkles and folds that can occur during placement.
6. Secure the AMNIOEXCEL Plus, when necessary, using the physician's choice of fixation (Steri-strips are provided).
7. Cover the AMNIOEXCEL Plus product with the non-adherent dressing
8. Optional: A saline-moistened bolster dressing is applied to ensure full contact with the wound bed.
9. Proceed with SOC dressings as described earlier.

Additional training will be supplied by an Integra team member either via onsite training or video conference. *Important note: Subject records must be maintained for the purpose of tracking tissue post-transplant per The Joint Commission on Accreditation of Healthcare Organizations and FDA requirements. The AMNIOEXCEL Plus ID number must be recorded in the recipient's medical record. Patient labels which include tissue numbers are contained in the AMNIOEXCEL Plus package to aid in the tracking process.*

In this study, the AMNIOEXCEL Plus will be covered with a non-adherent dressing and a saline moistened bolster applied, when appropriate, to ensure that the AMNIOEXCEL Plus is maintained with intimate contact to the wound bed. A foam dressing will be applied to cover the bolster and the dressings secured with conforming roller gauze. Finally, a cover dressing of Coban will be applied.

The dressing should be kept dry and will be changed once weekly during study visits. The subject will be instructed on the signs that indicate a need to seek medical attention.

6.1.2.3 RECOMMENDED INSTRUCTIONS FOR USE OF APLIGRAF²⁶

More information about application of the product can be found on manufacturer's website: [http://www.apligraf.com/professional/what is apligraf/how is it applied/index.html](http://www.apligraf.com/professional/what_is_apligraf/how_is_it_applied/index.html)

1. Wound Bed Preparation:
 - When applying Apligraf there should be no signs of infection (see Section 7.1 for subjects who become infected during the course of the study).
 - The wound bed should be prepared with appropriate method of debridement
2. Placement of the Apligraf®

- If desired, fenestrate Apligraf® with a knife blade or mesh (1.5-1 ratio). Apply Apligraf to wound and affix with method of preference i.e., Steri-Strips™, wound glue at periphery, or sutures
- 3. Primary Dressing
 - Cover Apligraf® with primary non-adherent dressing
- 4. Secondary Dressing
 - Apply appropriate dressing determined by wound type. A non-cytotoxic antimicrobial may also be applied at this time.
 - Provide Offloading for DFU
 - Keep dressing dry until first follow-up appointment.
- 5. First Follow-up
 - At Week 1 follow up, remove secondary dressing only for wound inspection and evaluation. Primary dressing (non-adherent) should be left undisturbed to facilitate integration of Apligraf®.
- 6. Application of Secondary Dressing
 - Reapply appropriate secondary dressings
- 7. Subsequent Follow-ups
 - On second follow up (14 days, Week 2), remove secondary and primary dressing for wound inspection and evaluation. Do not disturb or debride the wound bed. Perform light normal saline wash
- 8. Application of Primary and Secondary Dressings
 - Apply new primary (shown) and secondary dressings
 - On subsequent weekly follow-ups, continue to change primary and secondary dressings to monitor wound healing.
 - Apligraf may be reapplied if needed until wound healing is complete, as shown.

Additionally, the site should refer to Apligraf's Instructions for Use documents that are supplied with the product and/or consult an Apligraf representative for appropriate training.

6.2 HANDLING/STORAGE

AMNIOEXCEL PLUS

AMNIOEXCEL Plus Placental Allograft Membrane is provided in prescribed multiple geometric configurations. AMNIOEXCEL Plus Membrane is dehydrated during processing and should be visibly dry when the package is opened. The inner peel pouch and tissue product are terminally sterilized via E-beam irradiation and may be placed directly into the sterile field. Included in the packaging along with this insert are a Tracing Record and a set of patient labels.

- AMNIOEXCEL Plus is sterile and packaged for single patient, one time use only.
- Once opened, AMNIOEXCEL Plus must be used immediately or discarded.

AMNIOEXCEL Plus is to be stored in a clean, dry location at room temperature.

APLIGRAF

The site should refer to Apligraf's Instructions for Use documents that are supplied with the product and/or consult an Apligraf representative for information on appropriate handling and storage of the product.

CONTROL/STANDARD OF CARE SUPPLIES

All supplies for the SOC procedures can be kept at room temperature. General adherence to product expiration dates should be undertaken.

6.2.1 ACQUISITION AND ACCOUNTABILITY

Sites will be supplied by Integra with AMNIOEXCEL Plus and the SOC materials (i.e., boot, gauze, Coban, etc.) to be used with each of the investigational products. Specifically, sites will be provided with:

- Daily dressing kits used at home by all subjects during the Screening Phase of the study and if the subject is subsequently randomized to the SOC cohort.
- Weekly dressing kits used by the investigator on all subjects during the Treatment Phase of the study.

Important note: Subject records must be maintained for the purpose of tracking tissue post-transplant per The Joint Commission on Accreditation of Healthcare Organizations and FDA requirements. The AMNIOEXCEL Plus ID number must be recorded in the recipient's medical record. Patient labels which include tissue numbers are contained in the AMNIOEXCEL Plus package to aid in the tracking process.

Sites will purchase Apligraf from the manufacturer and order for arrival the day prior to the projected randomization date for every subject in the event that the subject is randomized to the Apligraf product. This purchase will be reimbursed by Integra.

Sites will document the use of all study products in the subject's medical records, in the required electronic case report forms (eCRFs), any applicable study logs.

6.3 MEASURES TO MINIMIZE BIAS: RANDOMIZATION AND BLINDING

This study will use randomization to minimize bias in this open label study. Randomization will occur in a 1:1:1 ratio and use a mixed block methodology. No blinding is possible. As well, no analytical blinding will occur during data review and/or analysis.

6.4 STUDY INTERVENTION COMPLIANCE

Subject compliance will be assessed by the site via standard didactic and interview methods. An initial training on dressing changes and application of the boot with the subject will occur on Screening Visit 1 (-12 weeks \pm 3 days). Compliance and subsequent (i.e., refresher) training will occur on each follow-up visit until the patient completes the study. This is shown in detail in the Table 2: Schedule of Activities.

6.5 CONCOMITANT THERAPY

Local Anesthesia (as required)

Debridement will be performed when appropriate on any study visit, at the discretion of the investigator. Debridement involves the use of a scalpel or other sharp implement to remove all dead and dying tissue on and around the ulcer. Debridement may involve the use of local anesthetics to reduce the possibility of pain the subject may feel during this procedure. The use of topical anesthetics is forbidden in this study.

All anesthetics should be documented on the Concomitant Medications eCRF.

NO other therapies such as devices, grafts, or medications which are **intended to improve wound healing** are permitted to be used on enrolled subjects.

[Intentionally Blank]

7 STUDY INTERVENTION DISCONTINUATION AND SUBJECT DISCONTINUATION/WITHDRAWAL

7.1 DISCONTINUATION OF STUDY INTERVENTION

For Subjects Who Develop an Infection:

Subjects who, during the course of the Treatment Phase, develop clinical signs and/or symptoms of infection (e.g., erythema, edema, pain, inflammation, increased drainage etc.) and in the opinion of the Investigator, require oral antibiotic therapy may receive a single course of oral antibiotics during the Treatment Phase of the study. **Should a second consecutive course be required/desired, the subject will be exited from the study.** This antibiotic therapy will be noted on the Concomitant Medications eCRF.

In addition to the above, for those subjects receiving Apligraf or AMNIOEXCEL Plus and develop signs/symptoms of infection, application of those allografts will be withheld on that visit. Application of allografts may be withheld for no more than 1 week at a time and no more than twice (non-consecutive visits) during the 12-week Treatment Phase. If signs and symptoms of infection requiring antibiotic therapy persist for more than one visit, or appear on more than 2 non-consecutive visits during the Treatment Phase, the subject will be discontinued from study participation.

For Subjects Whose Wound Closes:

Discontinuation from treatment in any of the study cohorts does not mean discontinuation from the study. There is one scenario in which a subject may continue in the study after intervention is final:

After treatment with AMNIOEXCEL Plus, Apligraf, and/or SOC **AND** if the subject's wound is documented as closed at or before week 12, the subject will continue to be monitored for two weeks to confirm wound closure. This is noted as week 13 and 14 in the Schedule of Activities, above, but may occur earlier.

If the subject's wound has NOT closed by week 12, the subject will be considered a study failure and will not have any further study visits.

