6 STUDY INTERVENTION

6.1 STUDY INTERVENTIONS ADMINISTRATION

6.1.1 STUDY INTERVENTION DESCRIPTIONS

6.1.1.1 INVESTIGATIONAL PRODUCTS (to be used with SOC products)

AMNIOEXCEL Plus

AMNIOEXCEL Plus tri-layer Placental Allograft Membrane (T-PAM) is a minimally manipulated placental membrane product made from tissues donated by pre-screened mothers during planned C-sections. AMNIOEXCEL Plus is intended for use as a wound covering. This product is an allograft tissue intended for homologous use for the repair, reconstruction, and replacement of skin at the direction of a physician.

More information can be found in the supplied Instructions for Use document that is included with the AMNIOEXCEL Plus product.

In this study, AMNIOEXCEL Plus will be applied weekly, in conjunction with SOC, as long as the ulcer remains open, or up to and including Week 11, whichever comes first. Note: In order to reduce the risk of complications, AMNIOEXCEL Plus should not be used in the presence of active infection. See Section 7.1 for instructions on treating infections as part of this trial.

Apligraf

Apligraf is a living, bi-layered skin substitute: the epidermal layer is formed by human keratinocytes and has a well-differentiated stratum corneum; the dermal layer is composed of human fibroblasts in a bovine Type I collagen lattice. While matrix proteins and cytokines found in human skin are present in Apligraf, Apligraf does not contain Langerhans cells, melanocytes, macrophages, lymphocytes, blood vessels or hair follicles.

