7.2 SUBJECT DISCONTINUATION/WITHDRAWAL FROM THE STUDY

Subjects are free to withdraw from participation in the study at any time upon request. As well, an investigator may discontinue or withdraw a subject from the study for the following reasons:

- If the subject's wound is open at follow-up week 1, the subject will be exited. They will be noted as having completed their study requirements.
- Significant study intervention non-compliance
- If any adverse event (AE), laboratory abnormality, or other medical condition or situation occurs such that continued participation in the study would not be in the best interest of the subject

- Anytime continued participation in the study is not in the best interest of the subject
- Disease progression which requires discontinuation of study participation
- Signs/symptoms of infection which require antibiotic therapy that persist more than 1 visit at a time or more than twice (non-consecutive visits) during the 12-week Treatment Phase.
- If the subject meets an exclusion criterion (either newly developed or not previously recognized) that precludes further study participation
- If the subject's site withdraws from the study
- If the Sponsor decides to stop the study

The reason for subject discontinuation or withdrawal from the study will be recorded on the appropriate eCRF. Subjects who sign the informed consent form and are randomized but do not receive the study intervention may be replaced.

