9.5. Missing Data

For primary efficacy evaluation of data points, the last available observation (LOCF) will be used. In the analyses of using the planimetry data, the last available planimetric value will be used for a discontinued subject. All subjects discontinued during the treatment period and before 100% wound closure during the treatment phase of the study will not be replaced and will be considered treatment failures for evaluating the primary and secondary endpoints.

10. Description of Other Variables and Analyses

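### Protocol Sections 7.1 and 7.2 give inconsistent infection rules for antibiotics, withholding and study exit, and because exit before closure counts as failure, the inconsistency can reach the primary endpoint

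*Protocol*

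**What the plan says.** **Protocol 7.1, first infection paragraph (all arms).** A subject with infection who needs oral antibiotics "may receive a single course of oral antibiotics during the Treatment Phase of the study". The exit rule is narrower: "Should a second consecutive course be required/desired, the subject will be exited from the study".

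**Protocol 7.1, second infection paragraph.** It opens by adding rules for subjects receiving Apligraf or AMNIOEXCEL Plus. Product is withheld at any visit with signs of infection, with a cap: "Application of allografts may be withheld for no more than 1 week at a time and no more than twice (non-consecutive visits". The paragraph ends with mandatory discontinuation from the study, on this trigger: "If signs and symptoms of infection requiring antibiotic therapy persist for more than one visit, or appear on more than 2 non-consecutive visits".

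**Protocol 7.2.** The same visit thresholds appear without any arm restriction, in a list headed by "an investigator may discontinue or withdraw a subject from the study for the following reasons". The list also contains a newly met exclusion criterion, if it precludes further participation. Exclusion 8 covers study-ulcer infection and systemic antibiotics for it.

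**Protocol 6.1.1.1.** "AMNIOEXCEL Plus should not be used in the presence of active infection"; a parallel sentence applies to Apligraf.

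**Protocol 7.1, on closed wounds.** The text says that stopping treatment is not the same as leaving the study. It then adds "There is one scenario in which a subject may continue in the study after intervention is final", and that scenario is a wound documented as closed by Week 12.

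**SAP 9.5.** Subjects discontinued in the treatment period before closure "will not be replaced and will be considered treatment failures for evaluating the primary and secondary endpoints".

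**The concern.** A site with an infected study ulcer needs one answer to three questions: may the subject have antibiotics again, may product be applied or withheld, and must the subject leave. The text gives more than one answer to the first and third. For one foreseeable case it gives no infection-specific answer to the second.

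This matters statistically because leaving before closure is scored as a failure. The trial is open label, so a discretionary exit is decided by someone who knows the arm. If sites treat the visit-based exit as compulsory for allograft subjects and optional for SOC subjects, the AMNIOEXCEL Plus versus SOC comparison partly reflects who was exited. AMNIOEXCEL Plus and Apligraf fall under the same text. There the risk is inconsistent application between sites, not a difference written into the rule.

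**Working it through.** **Step 1. The passages side by side.**

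(a) *Antibiotics.* Take a subject in any arm with separate infections, each treated and resolved, at Weeks 3 and 8.
- One course per Treatment Phase: the second course is not allowed.
- Exit at a second consecutive course: not triggered, because the courses are separate.
- Visit-based exit: not triggered, because two non-consecutive visits is not more than two.

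The second course is disallowed, yet no infection exit rule applies.

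(b) *Scope and force of the visit-based exit.* The thresholds in 7.1 and 7.2 agree. What differs is who is covered and whether exit is compulsory.

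| Reading of the 7.1 exit sentence | Allograft arms | SOC |
|---|---|---|
| Confined to its paragraph | mandatory | discretionary, through 7.2 |
| Applies to any subject | mandatory | mandatory, with 7.2 wrongly worded as discretionary |

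(c) *Signs lasting beyond one week without antibiotics.* Take an allograft subject with signs at two consecutive weekly visits. At the second visit product should not be used (6.1.1.1), and withholding for a further week exceeds the cap (7.1). The exit trigger is not met, because it needs infection requiring antibiotics. Only the general discretionary reasons in 7.2 remain.

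(d) *Stopping product versus leaving the study.* Section 7.1 separates the two, then names closure as the only case in which a subject continues after treatment ends.

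**Step 2. Route to the endpoint.** SAP 9.5 scores exit before closure as failure. The LOCF rule (Protocol 9.4.5, SAP 9.1) carries an open wound forward as open. Both give failure.

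**Step 3. The plan's own yardstick.** Protocol 9.2 states a 95% half-width of 13.5% at 90% closure and 38 per arm. This reproduces as the half-width for a difference between two arms: 1.96 × √(2 × 0.9 × 0.1 / 38) = 13.5 points. The single-arm Wald value is 1.96 × √(0.9 × 0.1 / 38) = 9.5 points. The difference is the right scale here, and nothing below depends on it.

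**Step 4. Possible size.** If infection, persistence and closure are alike in both arms, the closure rate lost by the allograft arm relative to SOC is r × s × c × k.

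- r, study-ulcer infection rate: 10–20%. Protocol 2.3.1 gives this band for suspected study-site wound infection in the manufacturer's Apligraf study. Using it for AMNIOEXCEL Plus and SOC is an assumption.
- s, share of infected subjects who meet the visit-based exit trigger: 25–100%, assumed.
- c, probability of closure had they stayed: 0.3–0.9, assumed.
- k, share of matching SOC cases kept in the study: 0 if the rule covers all arms, up to 1 if none are exited; assumed.

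Infected subjects per allograft arm: 38 × 0.10 = 3.8 to 38 × 0.20 = 7.6. Those exited: 38 × 0.10 × 0.25 = 0.95 to 38 × 0.20 × 1 = 7.6.

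| Case | r × s × c × k | Points against the allograft arm |
|---|---|---|
| Rule covers all arms | k = 0 | 0 |
| Low, half of SOC cases also exited | 0.10 × 0.25 × 0.5 × 0.5 | 0.6 |
| Low, no SOC case exited | 0.10 × 0.25 × 0.3 × 1 | 0.75 |
| Middle, half of SOC cases also exited | 0.20 × 0.5 × 0.6 × 0.5 | 3.0 |
| Middle, no SOC case exited | 0.20 × 0.5 × 0.6 × 1 | 6.0 |
| Extreme corner | 0.20 × 1 × 0.9 × 1 | 18 |

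The corner needs every infected allograft subject to meet the persistence or recurrence trigger and no matching SOC subject to leave. The second condition sets aside the antibiotic exit that is mandatory in all arms.

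**The case against.** A reader might infer that infected allograft subjects become failures while infected SOC subjects do not. The documents do not support that. An infection that resolves by the next visit, or that appears on up to two separate visits, does not trigger the visit-based exit. SOC subjects face the same mandatory exit at a second consecutive antibiotic course, share the 7.2 trigger, and are scored as failures in the same way.

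The contrast between mandatory and discretionary wording is also weaker than it looks. The permissive lead-in of 7.2 governs items that are plainly not optional, such as site withdrawal. The 7.1 exit sentence refers to the subject without naming an arm, under a heading for all subjects who develop an infection. It can be read as covering every arm. That the withholding cap applies only to allografts is inherent, since SOC has no product to withhold.

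The 10–20% band counts suspected infections, not infections that persist or recur, so 3.8 to 7.6 per arm cannot be taken as the number exited. Case (c) does not leave sites without any rule, because the general reasons in 7.2 apply. A permitted antibiotic course followed by exit if infection persists is a sequence, not a contradiction. The exclusion-criterion bullet is qualified, so its overlap with exclusion 8 is at most an ambiguity. Finally, discontinuations are summarised by arm and reason (SAP 10.2.1) and compared with Fisher's exact test (SAP 11.1.3), and the plan says that the study is not adequate for hypothesis testing.

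All of this stands, and it limits the claim about bias. It does not remove conflicts (a) and (d), the unclear scope in (b), or the gap in (c). Tabulating exits would show an imbalance without correcting it.

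**Conclusion.** The infection rules are inconsistent as written, and this holds without any numerical assumption. Because exit before closure is failure, the inconsistency can affect the primary endpoint.

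A bias in AMNIOEXCEL Plus versus SOC is conditional. It arises only if the 7.1 exit sentence is applied as allograft-only and SOC subjects in the same state are kept in. It would then run against the allograft arms. Its size cannot be established, since the documents give no infection rate for SOC or AMNIOEXCEL Plus and no persistence rate. Under the stated assumptions it runs from 0 to several points, with 3 to 6 in the middle case, beside the plan's 13.5-point half-width. The 18-point corner should not be quoted as an estimate.

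This is a should-fix. The textual conflict is certain, while the effect on the comparison is possible and unmeasured.

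**What to change.** **Protocol.** Reconcile both infection paragraphs of 7.1 with the infection and exclusion-criterion bullets of 7.2 and with exclusion 8, so that they form one consistent text. The sponsor's clinicians choose its content. For each exit sentence, state which arms it covers and whether it is mandatory or discretionary. Reconcile the two statements in 7.1 on whether stopping product ends study participation.

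**Analysis.** Report infection-related exits by arm. Beside the SAP 9.5 failure rule, give a sensitivity analysis of the primary endpoint that uses the last observed closure status and any later status collected. For subjects exited with an open wound, the last observed status alone reproduces failure. The analysis is therefore informative only where later status exists. Where it does not, show the result across assumed closure of these exits, from none to all, by arm.

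**Cost.** Amendment wording, one table and one sensitivity analysis. Exit reasons are already recorded under Protocol 7.2. SAP Section 12 reports the photograph review as done, so an amendment may come too late to guide sites. In that case, document how sites applied the rules and keep the analysis part.
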